3.1 Design

The study is a multicenter prospective open labeled randomized controlled trial. Elderly patients with age ≥ 65 years and received hemodialysis treatment for more than 6 months will be included in the study. After enrollment, the patients will be educated about how to keep diet records and then they will be randomly divided into group A and group B in a 1:1 ratio. The patients in group A will receive oral postbiotics and group B receive placebo. The treatment period is 12 weeks. Subsequently, group A ends the trial, and group B enters the remedial treatment period, receiving oral postbiotics, and the treatment cycle is 12 weeks. At 0, 12th and 24th week, quality of life score, nutrition evaluation, diet status and gastrointestinal symptom score of patients will be evaluated. The stool and serum of patients will be collected for intestinal flora and urotoxins IS, PCS and TMAO measurements. The improvement of biochemical indicators will be evaluated. The biochemical indicators include blood creatinine, urea nitrogen, albumin, prealbumin, hemoglobin, blood calcium, blood phosphorus, whole parathyroid hormone, blood potassium, C-reactive protein, ferritin, transferrin saturation, et al. During the whole intervention process, patients will be encouraged to maintain intake of protein and fiber and keep a diet log.

During the intervention process, the process of hemodialysis and other diagnosis and treatment behaviors will be performed according to clinical routine.

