3.3 Population

3.3.1 Participation Criteria

Inclusion criteria:

Investigators must maintain a screening log of all potential study candidates that includes limited information about the potential candidate, date, and outcome of the screening process (e.g. enrolled into study, reason for ineligibility, or refused to participate). After signing an informed consent form, potential patients must meet all of the criteria:

1. Age ≥ 65 years.
2. Receiving maintenance hemodialysis therapy for at least 6 months.

Exclusion criteria:

The following exclusion criteria must NOT be present for each subject:

1. Subjects with medical history that might affect oral feeding (e.g. intestinal obstruction, gastrointestinal bleeding, acute pancreatitis and accidental inhalation) within the last 1 month prior to screening.
2. Subjects with medical history that might affect gastrointestinal functions (e.g. inflammatory bowel disease (IBD), irritable bowel syndrome (IBS), short bowel syndrome (SBS), et al.).
3. Subjects who cannot communicate and collaborate normally.

3.3.2 The source and method of population selection.

The study will select the patients who are ≥ 65 years old and receive long-term hemodialysis treatment in the hemodialysis center, and their clinical manifestations should meet the eligible criteria. We will communicate with the patients about the content and significance of the study, and patients who agree to sign the informed consent will finally be included in the study.

3.3.3 Follow-up.

The schedule of follow-up visits is shown in the flowchart below.

The Study Flowchart

		Screening period	Introduction Period	Treatment Period 1 st to 12 th Week			Remedial Treatment Period (Only Group B) 13 th to 24 th Week		
		Follow-up 1	Follow-up 2	Follow-up 3	Follow-up 4	Follow-up 5	Follow-up 6	Follow-up 7	Follow-up 8
Follow-up Time Window		-4 th to -2 nd week	-2 nd to 0 week	4 th week	8 th week	12 th week	16 th week	20 th week	24 th week
Eligibility Criteria	Medical History	✓							
	Medicine Prescription	✓				✓			✓
	Hemodialysis Parameter	✓							
Signature of Informed Consent		✓							
Demographic Data		✓							
Kt/V			✓	✓	✓	✓	✓	✓	✓
URR			✓	✓	✓	✓	✓	✓	✓
3-Day Diet Records			✓			✓			✓
Height, Weight, BMI			✓			✓			✓
Upper Arm			✓			✓			✓

Circumference, Upper Arm Skin Fold Thickness								
Grip Strength (Non-Fistula Side)		√			√			√
Abdominal Fat		√			√			√
Body Composition Analysis (Bioresistive Method)		√			√			√
Nutritional Scores (SGA-7)		√			√			√

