3.3.3.3 Treatment Period (1st to 12th Week)

Follow-up visits are scheduled at every 4 weeks in the treatment period. The following list summarizes the procedures for the treatment period:

- We should ask patients about any adverse events and changes in medication after last follow-up visit.
- We should record any change of dialysis prescription.
- We should record any problem of hemodialysis device, dialyzer and hemodialysis line.
- We should record the diet of patients in the 12th week.
- We should score the rating scales in the 12th week.
- We should perform the anthropometric measurements in the 12th week.
- We should collect the blood and stool samples for urotoxins and intestinal flora measurements in the 12th week.
- We should collect the results of recent routine blood test before dialysis of the patient in the 4th, 8th and 12th week.
- We should ensure whether the patient has still met the eligibility criteria. If so, supply the medicine at the original dose. If not, remove him/her from the group.

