3.3.3.4 Remedial Treatment Period (13th to 24th Week)

Group A end the trial and group B enter the remedial treatment period. Follow-up visits are scheduled at every 4 weeks in the remedial treatment period. The following list summarizes the procedures for the remedial treatment period:

- We should ask patients about any adverse events and changes in medication after last follow-up visit.
- We should record any change of dialysis prescription.
- We should record any problem of hemodialysis device, dialyzer and hemodialysis line.
- We should record the diet of patients in the 24th week.
- We should score the rating scales in the 24th week.
- We should perform the anthropometric measurements in the 24th week.
- We should collect the blood and stool samples for urotoxins and intestinal flora measurements in the 24th week.

- We should collect the results of recent routine blood test before dialysis of the patient in the 16th, 20th and 24th week.
- We should ensure whether the patient has still met the eligibility criteria. If so, supply the medicine at the original dose. If not, remove him/her from the group.

3.3.3.5 Termination.

Patients who complete 24 weeks of follow-up visits are allowed to continue or discontinue their medication supply at the end of the study.

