3.6 Sample Size

The study is a randomized control trial. There is no previous related published study so that it's an exploratory trial. According to the study of other micro ecological preparations, the sample size of each group should be 20. Taking into consideration the dropout rate of 20% by the end of the study, a sample size of 30 per group is planned for this study.

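### The eligibility re-check in 3.3.3.3 removes randomised patients without keeping their week-12 assessment; the likely bias is small and one sentence would prevent it

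*Protocol*

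**What the plan says.** Protocol 3.3.3.3 lists an eligibility re-check among the procedures of the treatment period, whose visits fall at weeks 4, 8 and 12. The consequence is "If so, supply the medicine at the original dose. If not, remove him/her from the group". One branch concerns supply and the other concerns membership of the group.

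The primary outcomes in 3.4.1 are nutritional status (physical examination and SGA-7) and quality of life (GSRS, TM-SF36 and EFS). In the treatment period these are measured once: "We should score the rating scales in the 12th week" and "We should perform the anthropometric measurements in the 12th week". Section 3.1 agrees: "At 0, 12th and 24th week, quality of life score, nutrition evaluation, diet status and gastrointestinal symptom score of patients will be evaluated". Group A leaves the trial after week 12, so week 12 is the only post-baseline point of the randomised comparison.

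Nothing else says what happens to a removed patient. Section 3.3.3.5 covers completers only: "Patients who complete 24 weeks of follow-up visits are allowed to continue or discontinue their medication supply at the end of the study". The flowchart in 3.3.3 has no early-exit visit.

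**The concern.** Eligibility criteria decide who enters a trial. Applied again after randomisation, with removal as the result, they select patients on events that happen after allocation. If removal also ends assessment, the week-12 comparison is made among those who stayed eligible and no longer between the groups as randomised.

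Two features make this more than a loss of numbers. First, there is no interim primary score to fall back on, and an analysis plan cannot recover a week-12 score that was never collected. Second, the events that trigger removal overlap with the outcomes. New gastrointestinal disease bears on the GSRS and on the gastrointestinal item of the SGA-7. Inability to communicate bears on the EFS clock test. Patients lost this way may therefore score differently from those who stay.

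**Working it through.** **Which criteria can lapse (3.3.1).**
- Age of 65 or over cannot lapse.
- Exclusion 1 is fixed in time, "gastrointestinal bleeding, acute pancreatitis and accidental inhalation) within the last 1 month prior to screening", so read literally it cannot newly fail.
- Exclusion 2 can newly arise: "Subjects with medical history that might affect gastrointestinal functions".
- Exclusion 3 (unable to communicate and collaborate) can newly arise.
- The inclusion criterion of maintenance haemodialysis can lapse if a patient leaves haemodialysis.

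**Which visits matter.** Only removals at weeks 4 and 8 threaten the primary scores. At week 12 the scores are due at the same visit.

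**Size.** The protocol gives no removal rate, so there is no figure of its own to reproduce. Its only figure for loss is in 3.6: "Taking into consideration the dropout rate of 20% by the end of the study". With 30 per group this is 0.20 × 30 = 6 patients per arm from all causes.

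Inputs:
- 30 per group (3.6) and a 5% significance level (3.8).
- Assumed: a two-sided t test and no true effect.
- Assumed: removed patients are g = 0.5 or 1 SD worse than the mean of their whole arm.

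If k of 30 patients in an arm are removed, the mean of those who stay looks better by g × k/(30 − k). The shift in the difference between arms is

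shift = g × [kA/(30 − kA) − kB/(30 − kB)],

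in favour of the arm with more removals. Its standard error in SD units is √(1/nA + 1/nB), where n is the number remaining. The false-positive rate comes from the noncentral t distribution with noncentrality shift/SE.

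| Removed (one arm v other) | SE | Shift, g = 1 | False positive, g = 1 | Shift, g = 0.5 | False positive, g = 0.5 |
|---|---|---|---|---|---|
| 1 v 0 | 0.260 | 1/29 = 0.034 | 5.2% | 0.017 | 5.1% |
| 2 v 0 | 0.263 | 2/28 = 0.071 | 5.8% | 0.036 | 5.2% |
| 3 v 0 | 0.265 | 3/27 = 0.111 | 7.0% | 0.056 | 5.5% |

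Removals in both arms partly cancel. At g = 1, 2 v 1 gives 2/28 − 1/29 = 0.037 SD and 3 v 1 gives 3/27 − 1/29 = 0.077 SD. Equal numbers with equal g give 0.

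If g is measured against the patients who stay, the shift is g × (kA − kB)/30. At g = 1 that is 0.033, 0.067 and 0.100 SD for 1, 2 and 3 v 0, so the conclusion does not depend on this choice.

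For scale, the difference detectable with 80% power is 0.74 SD with 30 per arm. The largest shift in the table is 0.111/0.74, about 15% of that.

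**The case against.** The strongest reply is that the sentence is only about supply. It is the alternative to continuing supply, and the week-12 scoring instruction in the same list is not limited to patients still being supplied. On that reading nothing is lost. The reading is possible, but the protocol does not state it. The words speak of leaving the group, and sites in a multicentre trial could take them either way.

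The second reply is that the rule will rarely apply, and this stands. Few criteria can lapse and only two visits matter. The flowchart ticks medical history under eligibility at the first visit only. Some of the affected patients would be lost anyway: someone who cannot communicate may be unable to complete the self-completed quality-of-life scale or the EFS clock test whatever the rule says. Precision is not at risk either, since 30 per group exceeds the 20/(1 − 0.20) = 25 that the inputs in 3.6 imply.

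A reader might infer a moderate bias by letting the rule account for the whole dropout allowance in one arm. At g = 1, 6 v 0 gives 6/24 = 0.25 SD and a false-positive rate of 14.6%. The protocol does not support this. Its 20% is for all causes and is not said to fall on one arm.

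A reader might also infer that staff will apply the re-check differently by arm, because 3.1 calls the trial open label. However, 4.2 describes a placebo and 5.1 a blind analysis, so masking is described inconsistently. Arm-dependent judgement is possible and not shown. Without it, and without a product effect on eligibility, chance imbalances go either way and the overall false-positive rate stays at 5%.

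**Conclusion.** The point holds as a weakness in conduct with a small likely effect. In its ordinary sense, 3.3.3.3 excludes patients after randomisation for reasons partly related to the primary scales, and nothing in the protocol keeps their week-12 scores.

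Under the assumed gap of 0.5 to 1 SD, one to three removals in one arm only give a shift of about 0.02 to 0.11 SD and a false-positive rate of about 5% to 7%. Those rates are conditional on the one-sided pattern. The shift is zero if removals are alike in number and prognosis, and it can run for or against the product. Removal counts and the gap are both assumptions.

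Two wider readings are not supported. The absence of an analysis-set rule is no fault here, because such a rule may sit in an analysis plan that is not shown. The identical sentence in 3.3.3.4 concerns group B after the randomised comparison and does not touch the primary result.

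**What to change.** Leave the decision on supply as the protocol has it. In 3.3.3.3, replace the removal clause with wording to this effect: the patient remains in the randomised group, is asked to attend the week-12 assessments where able, and has the date and reason for ending supply recorded by arm. How these patients enter the analysis may be set in the SAP.

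The cost is one sentence and a few additional week-12 assessments, some of which may need a separate visit for patients no longer on haemodialysis. The estimate may be somewhat diluted by patients who stopped the product, and some scores will still be missing where a patient cannot complete the scales.

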3.3.3.4 Remedial Treatment Period (13th to 24th Week)

Group A end the trial and group B enter the remedial treatment period. Follow-up visits are scheduled at every 4 weeks in the remedial treatment period. The following list summarizes the procedures for the remedial treatment period:

- We should ask patients about any adverse events and changes in medication after last follow-up visit.
- We should record any change of dialysis prescription.
- We should record any problem of hemodialysis device, dialyzer and hemodialysis line.
- We should record the diet of patients in the 24th week.
- We should score the rating scales in the 24th week.
- We should perform the anthropometric measurements in the 24th week.
- We should collect the blood and stool samples for urotoxins and intestinal flora measurements in the 24th week.

- We should collect the results of recent routine blood test before dialysis of the patient in the 16th, 20th and 24th week.
- We should ensure whether the patient has still met the eligibility criteria. If so, supply the medicine at the original dose. If not, remove him/her from the group.

3.3.3.5 Termination.

Patients who complete 24 weeks of follow-up visits are allowed to continue or discontinue their medication supply at the end of the study.

3.4 Outcomes

3.4.1 Primary Outcome Measure:

Outcome Measure	Measure Description	Time Frame
Changes of nutritional status from the baseline to the end of treatment and differences between the intervention group and the placebo group.	Nutritional status of the patient is defined as the results of physical examination and SGA-7 rating scale.	From the baseline to the end of treatment.
Changes of quality of life from the baseline to the end of treatment and differences between the intervention group and the placebo group.	Quality of life of the patient is defined as the scores of gastrointestinal symptom rating scale (GSRS), kidney disease life quality scale (TM-SF36) and enervation frailty scale (EFS).	From the baseline to the end of treatment.

3.4.2 Secondary Outcomes:

Outcome Measure	Measure Description	Time Frame
Changes of enterogenous urotoxin level from baseline to the end of treatment and difference between the intervention and placebo group.	Enterogenous urotoxin level is defined as the serum level of IS, PCS and TMAO. The levels of serum IS, PCS and TMAO will be measured by mass spectrometry.	From the baseline to the end of treatment.

Changes of intestinal flora structure from the baseline to the end of treatment, and the difference between the intervention group and the placebo group.
	
The structure of intestinal flora will be measured by the V3-V4 region of 16S rDNA with MiSeq PE300 sequencing platform for high-throughput analysis and described by number of the flora.
	
From the baseline to the end of treatment.

Changes of routine biochemical indicators from the baseline to the end of treatment, and differences between the intervention group and the placebo group.
	
The routine biochemical indicators include serum creatinine, urea nitrogen, albumin, prealbumin, hemoglobin, serum calcium, blood phosphorus, total parathyroid hormone, serum potassium, carbon dioxide, C-reactive protein, ferritin, transferrin saturation.
	
From the baseline to the end of treatment.

Changes of dietary intake from the baseline to the end of treatment, and the difference between the intervention group and the placebo group.
	
Dietary intakes of the patients will be described by the diet record.
	
From the baseline to the end of treatment.

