3.8 Statistical Analysis

Descriptive statistics for continuous variables will include questionnaire score, anthropometric and biochemical indicators, fecal flora structure and urotoxins level. They will be expressed as mean \pm standard deviation and median. Analysis of categorical variables will include frequency and percentage.

In analytical statistics, the distribution type of data will be initially considered when we determine the reference range, and then we will calculate the unilateral lower limit P5. We will compare the distribution of the variables between the normal population and the patients in the two groups with Independent t test, Chi-square test /Fisher exact test, one-way ANOVA and non-parametric analysis. We will analyze the relationship between exposure and outcome with Logistic regression and Cox

regression, including univariate and multivariate regression. In multivariate regression analysis, the selected variables include important general clinical data, the variables clearly associated with the outcome, and the variables analyzed as $P < 0.1$ in univariate regression.

Statistical analyses will be performed using Statistical Package for Social Science (SPSS) for Windows version 23.0 (SPSS Inc. Chicago, IL). Statistical mapping will be performed using GraphPad Prism v.8 (La Jolla, CA, USA) and R 4.1.0 (The R Foundation, Vienna, Austria). Sample size estimation will be performed using PASS 2021 (UT, USA).

$P < 0.05$ is considered statistically significant. All confidence intervals are stated at the 95% confidence level.

4. Subject Protection

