4.3 Confidentiality

This study mainly collects the required data before and after treatment for efficacy observation. Personal data in the study are confidential. The blood samples are routine clinical laboratory items, and all are daily clinical work. The laboratory department will handle them according to the routine clinical laboratory. Researchers are required to keep the identity of the subjects confidential. Clinical data and records of the subjects will be kept in a locked filing cabinet and will be accessible only to the investigator. No personal data is disclosed at publication. There are no potential conflicts of interest and no special people involved in this study. The personal data of the subjects in the study will be confidential, and their blood samples will be coded by a unique number rather than their name. No identifying information will be disclosed to anyone other than the researchers, and all researchers are required to keep their identities confidential. In order to ensure that the study is carried out in accordance with the regulations, members of the government management department or the ethics committee can access the personal data of the subjects if necessary, and the process will also strictly follow the principle of confidentiality. No personal information about any subjects will be disclosed when the results of this study are published.

5. Quality Control

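### The outcome definitions join change from baseline and the arm difference without saying that the randomised contrast decides efficacy, so a within-arm change could be read as a result in its own right.

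*Protocol*

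**What the plan says.** Protocol section 3.4 lists two primary and four secondary outcomes. The primary outcomes are "Changes of nutritional status from the baseline to the end of treatment and differences between the intervention group and the placebo group" and "Changes of quality of life from the baseline to the end of treatment and differences between the intervention group and the placebo group". The first secondary outcome is "Changes of enterogenous urotoxin level from baseline to the end of treatment and difference between the intervention and placebo group". The rows for intestinal flora, biochemistry and dietary intake use the same two-part form. In all six rows the change and the arm difference are joined by the word and, with no order of priority.

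Section 3.8 gives the group comparison as "We will compare the distribution of the variables between the normal population and the patients in the two groups with Independent t test", followed by chi-square or Fisher's exact test, one-way ANOVA and unspecified non-parametric analysis. It sets P<0.05 as the threshold. It names no paired test, and no comparison of change between arms. Its multivariable models are logistic and Cox regression.

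Two design features bear on how a within-arm change should be read. Under section 3.1, "During the whole intervention process, patients will be encouraged to maintain intake of protein and fiber and keep a diet log"; this applies to both arms. Under section 3.3.3.4, group A leaves the trial after week 12 and only group B is followed, on the product, to week 24.

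**The concern.** A change from baseline in one arm mixes any product effect with everything else that happens to that arm over 12 weeks. Here that includes placebo response, the attention of repeated scoring and four-weekly visits, and the encouragement about intake and diet logging. Only the comparison of randomised arms removes what the arms share.

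Because 3.4 names both quantities and ranks neither, a report could present a significant improvement in group A against its own baseline as a primary result. It could also contrast significance in A with non-significance in B, which is not a test of the difference between the arms. Weeks 13 to 24 raise the same question more sharply, because group B then has no concurrent control and before-after change is all that can be computed. At stake is whether a small exploratory trial reports a signal that its own control arm does not support.

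**Working it through.** **The text.** The protocol gives no figure for this point, so there is none to reproduce. Read side by side, all six rows of 3.4 name the change and the arm difference, and none makes the arm difference decisive. Section 3.8 does not close the gap. Its group tests are unadjusted and are not tied to a change score or to a time point. Logistic and Cox regression need a binary or time-to-event outcome, whereas the scores, toxin levels and laboratory values in 3.4 are measured quantities.

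**How far a within-arm reading could mislead.** This calculation is illustrative.

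Inputs:
- Planned size 30 per group and 20% dropout (section 3.6), so completers per arm = 30 × (1 − 0.20) = 24. The values 20 (the stated requirement) and 30 (no dropout) serve as a range.
- P<0.05 (section 3.8). Two-sided testing is assumed, because the section does not say.
- True product effect: zero (the scenario under test).
- Shared improvement d, in SDs of the change score, equal in both arms. This is an assumption, since the protocol gives no value. The range is 0 to 0.5.
- A paired t test within each arm. This is also an assumption, since 3.8 names none.

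Formula: p = P(T > t₀.₉₇₅,ₙ₋₁), where T is noncentral t with n − 1 degrees of freedom and noncentrality d√n. For n = 24 the critical value is 2.069 and √24 = 4.899. The arms are independent, so the probability that A is significantly improved and B is not is p(1 − p).

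| d | d√24 | p: A significantly improved | p(1 − p): A but not B |
|---|---|---|---|
| 0 | 0 | 0.025 | 0.024 |
| 0.2 | 0.98 | 0.154 | 0.130 |
| 0.3 | 1.47 | 0.291 | 0.206 |
| 0.4 | 1.96 | 0.467 | 0.249 |
| 0.5 | 2.45 | 0.650 | 0.227 |

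For d of 0.2, 0.3 and 0.5, p is 13%, 25% and 56% with n = 20, and 18%, 36% and 75% with n = 30.

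The shared improvement cancels in the between-arm t test on change, which therefore keeps its nominal error: 5% two-sided, 2.5% in favour of A. In 100,000 simulated trials with n = 24 per arm, the rate in favour of A was 2.6%, 2.4% and 2.5% at d = 0, 0.3 and 0.5. The rate of A significant and B not was 2.4%, 20.6% and 22.8%, in agreement with the table.

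**The case against.** The strongest reply is that each row of 3.4 is one outcome with one time frame, and that its natural sense, in what may be translated wording, is change from baseline compared between arms. That may be the intent, and the absence of a paired test from 3.8 fits it. The reply shows that the wording is ambiguous. It does not show that the protocol settles the matter.

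A second reply is that baseline adjustment and the reporting of within-arm changes belong in a statistical analysis plan, which may exist. That is fair for the details. Which contrast defines a primary outcome, however, is something this protocol sets out to state, and it does so unclearly. The exploratory status in 3.6 lowers the stakes but does not remove the need, since the trial has a placebo arm and a significance threshold.

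A reader might infer more than the documents support:
- *That the plan tests within-arm change at P<0.05, or accepts significance in A alone as success.* Section 3.8 names no such test and no such rule.
- *That section 4.3 ties efficacy to a before-after reading*, because it says "This study mainly collects the required data before and after treatment for efficacy observation". The sentence sits in the confidentiality section and describes what is collected. A between-arm comparison of change needs the same data.
- *That both arms are coached to eat better.* The education is about how to keep records, and the encouragement is to maintain intake.
- *That regression to the mean will lift both arms.* Eligibility in 3.3.1 rests on age, time on hemodialysis, gastrointestinal history and ability to cooperate. It selects on no outcome value, so there is no basis for expecting a group-level shift.

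**Conclusion.** The point holds as a defect of definition. Section 3.4 does not make the randomised contrast decisive for any of its six outcomes, and 3.8 does not supply that contrast. A within-arm change could therefore be read as a result.

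The size depends on two things the protocol does not give: use of a paired within-arm test, and a shared improvement. With a shared improvement of 0.2 to 0.5 SD, 24 completers per arm and no product effect, group A looks significantly improved in 15% to 65% of trials, against 2.5% for the between-arm test. With no shared change the two agree at 2.5%, so the figures describe a risk if the wording is read that way, not an error rate of the plan as written. The case for clarifying the wording does not depend on where in that range the truth lies.

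**What to change.** In section 3.4, define each outcome as the difference between group A and group B at week 12, adjusted for the baseline value of the same measure (for example by ANCOVA). Week 12 is the last visit at which both arms are followed under their randomised allocation.

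In section 3.8, name that contrast. Add that within-arm changes, including those in group B over the uncontrolled weeks 13 to 24, are descriptive and do not support an efficacy conclusion.

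The baseline and week 12 measurements are already scheduled, so visits, sample size and treatment stay as they are. The cost is a wording amendment to two sections. The downside is that there will be fewer nominally significant results to report.
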